3.2.4 Follow-up Period

Follow-up Period will include discontinuation assessments and off-treatment visit. Subject will discontinue study treatment if he/she qualifies for any of the criteria listed in Section 9.3.3.1. The discontinuation assessments will occur within 7 days and off-treatment visit on 30th day (+ 7 days) after final dose of study treatment.

4 DETERMINATION OF SAMPLE SIZE

The primary objective of this study is to investigate the tolerability and safety of lenvatinib in combination with everolimus. Hence neither clinical hypothesis nor judgment criteria are set, the sample size is not based on statistical consideration. The 6 to 12 subjects per initial dose group are considered to be adequate to obtain some preliminary data for the assessment of safety.

5 STATISTICAL METHODS

All descriptive statistics for continuous variables will be reported using mean, standard deviation (SD), median, minimum and maximum. Categorical variables will be summarized as number (percentage) of subjects.

All analysis will be performed for total subjects and by initial dose group (if applicable).

5.1 Study Endpoints

5.1.1 Primary Endpoint

- DLTs
- Safety endpoints (adverse events, clinical laboratory parameters, vital signs, weight, 12-lead ECG, ECOG-PS and left ventricular ejection fraction [LVEF])

5.1.2 Secondary Endpoints

- PK parameters of lenvatinib and everolimus
- Best overall response (BOR), objective response rate (ORR), disease control rate (DCR), and percent change from baseline in the sum of the diameters of target lesions (if applicable).

5.1.2.1 Pharmacokinetic (PK) Endpoints

PK parameters derived by non-compartmental analysis using plasma concentrations of lenvatinib and blood concentrations of everolimus which include, but are not limited to, are shown as below:

C_{\max}	maximum observed concentration
t_{\max}	time at which the highest drug concentration occurs
$AUC_{(0-t)}$	area under the concentration-time curve from zero time to time of last quantifiable concentration
$AUC_{(0-t_i)}$	area under the concentration-time curve from zero (pre-dose) to a given sampling time (t_i)
$AUC_{(0-\infty)}$	area under the concentration-time curve from zero time extrapolated to infinite time
$t_{1/2}$	terminal elimination phase half-life
CL/F	apparent total clearance following oral dosing
V_z/F	apparent volume of distribution at terminal phase

$C_{ss,max}$	maximum observed concentration at steady state
$C_{ss,min}$	minimum observed concentration at steady state
$t_{ss,max}$	time at which the highest drug concentration occurs at steady state
$AUC_{(0-\tau)}$	area under the concentration-time curve over the dosing interval
CL_{ss}/F	apparent total clearance following oral administration at steady state
$C_{ss,av}$	average steady-state concentration
$R_{ac}(C_{max}), R_{ac}(AUC)$	accumulation index
PTF ratio	peak-trough fluctuation ratio

5.2 Study Subjects

5.2.1 Definitions of Analysis Sets

DLT Analysis Set is the group of subjects who have completed treatment Cycle 1 without major protocol deviation with at least 75% of treatment compliance and were assessed for DLT, and subjects who have experienced DLT during Cycle 1. Subjects with less than 75% treatment compliance to lenvatinib or everolimus due to a reason other than toxicity up to Cycle 1 Day 28 will not be included in this analysis set.

Safety Analysis Set/Efficacy Analysis Set is the group of subjects who received at least 1 dose of lenvatinib

Pharmacokinetic Analysis Set is the group of subjects who received at least 1 dose of lenvatinib and had sufficient PK data to derive at least 1 PK parameter.

The number of subjects enrolled, the number and the percentage of subjects included in each analysis set will be presented. Subject data listings will be provided.

5.2.2 Subject Disposition

Screening subjects table will include the number of subjects who are enrolled (i.e., subjects who signed informed consent), failed screening, and the primary reason for screen failures. Subject disposition table will include the number of subjects who are treated, completed/discontinued the study. Similarly, the number of subjects who completed/discontinued the study treatment, and the primary reason for the study treatment discontinuation will also be summarized.

A subject who completed the study is defined as whose DLT assessment has been completed adequately. A subject who completed the study treatment is defined as who discontinued study treatment due to radiological or disease progression or were on-going at the study cut-off.

Subject data listings will be provided.

5.2.3 Protocol Deviations

Major protocol deviation criteria will be established and subjects with major protocol deviations will be identified and documented before the database lock. All protocol deviations identified according to study entry criteria and during treatment will be presented in the clinical study report (CSR).

5.2.4 Demographic and Other Baseline Characteristics

Demographic and other baseline characteristics for the Safety Analysis Set and Pharmacokinetic Analysis Set will be summarized using summary statistics. Continuous demographic and baseline variables include age, height, and weight; categorical variables include sex, race, ethnicity, ECOG PS, NYHA, diagnostic information (metastatic sites, number of metastatic site, histological type, time since RCC diagnosis to first dose of study treatment, TNM categories and stage), prior therapy (nephrectomy [yes or no], radiotherapy [yes or no], sites of radiotherapy, anti-cancer medication [yes or no], type of anti-cancer medication [axitinib, everolimus, and so on.], number of VEGF targeted therapy [1 regimen, 2 regimens, 3 regimens] and other therapies [yes or no]), treatment duration and reason for discontinuation of last anti-cancer medication, hypertension (yes or no), and creatinine clearance (\geq LLN, $<$ LLN and ≥ 60 mL/min, and 60-40 mL/min).

The categories for metastatic site, site of previous radiotherapy, type of prior anti-cancer medication depend on actual data.

Subject data listings will be provided.

5.2.5 Prior and Concomitant Therapy

All investigator terms for medications recorded in the case report form (CRF) will be coded to an 11-digit code using the World Health Organization Drug Dictionary (WHO DD). The number (percentage) of subjects who took prior and concomitant medications will be summarized on the Safety Analysis Set by Anatomical Therapeutic Chemical (ATC) class (anatomical class, pharmacological class, and pharmacological sub-class) and WHO DD preferred term. Prior medications are defined as medications that stopped before the first dose of study treatment. Concomitant medications are defined as medications that (1) started before the first dose of study treatment and were continuing at the time of the first dose of study treatment, or (2) started on or after the date of the first dose of study treatment up to 30 days after last dose. Medications received after 30 days of last dose will be considered as post treatment medications. All medications will be presented in subject data listings.

5.2.6 Treatment Compliance

Treatment related protocol deviations will be presented in CSR as provided in section “[5.2.3 Protocol Deviations](#)”.

5.3 Data Analysis General Considerations

5.3.1 Pooling of Centers

Subjects from all centers will be pooled for all analyses.

5.3.2 Adjustments for Covariates

No adjustment for covariates will be performed.

5.3.3 Multiple Comparisons/Multiplicity

No statistical comparison is planned in this study.

5.3.4 Examination of Subgroups

No subgroup analysis is planned in this study.

5.3.5 Handling of Missing Data, Dropouts, and Outliers

No imputation will be performed for missing data.

5.3.6 Other Considerations

Not applicable.

5.4 Efficacy Analyses

5.4.1 Primary Efficacy Analysis

Since this study is phase 1, primary endpoint is not defined.

Efficacy analyses will be based on the Efficacy Analysis Set. Based on the tumor assessments according to response evaluation criteria in solid tumor (RECIST) 1.1, BOR will be summarized. BOR are complete response (CR), partial response (PR) stable disease (SD), progression of disease (PD) and not evaluable (NE). ORR, DCR and their corresponding 2-sided 95% confidence intervals (CIs) will be calculated using Cropper-Pearson's exact method. ORR is defined as the proportion of subjects who achieved BOR of CR or PR. DCR is defined as the proportion of subjects who achieved BOR of CR, PR or SD. Subjects with non-target disease only will be assigned to SD category if the BOR is non-CR/non-PD. SD has to be achieved at ≥ 7 weeks after first dose. CR and PR do not have to be confirmed at ≥ 4 weeks later assessment. If applicable, a spaghetti plot will be presented for the percent changes from baseline in the sum of the diameters of target lesions by subject.

Median, Q1, and Q3 for progression free survival (PFS) with its 95% CI will be evaluated. The number (percentage) of subjects with event/censored will be summarized. The PFS rate with its 95% CI at 4-month, 8-month and 12-month will be calculated using Kaplan-Meier

product limit estimates, if applicable. Kaplan-Meier plots with the number of subjects at risk will be presented for PFS.

PFS is defined as the time from the date of first dose to the date of first documented PD or death due to any cause (whichever occurs first). For subjects who do not have an event (documented PD or death from any cause), PFS will be censored. Censoring rules for PFS are shown in [Table 2](#).

PFS (days) = Date of first documented PD/ death/ Censored date – Date of first dose + 1.

Table 2 Censoring Rule of PFS

Situation	End Date	Censor/Event
Documented PD during the study	Date of the first assessment of the series of the tests that determined PD	Event ^a
Death during the study before PD	Date of death	Event ^a
No baseline or unreadable baseline tumor assessments	Date of first dose	Censor
Treatment discontinuation for other than PD or death, and no postbaseline tumor assessments	Date of first dose	Censor
Treatment discontinuation for other than PD or death with postbaseline tumor assessments	Date of last adequate ^b tumor assessment	Censor
New anticancer treatment started prior to PD or death	Date of last adequate ^b tumor assessment prior to or on date of new treatment	Censor
PD or death after two or more missed tumor assessments ^c	Date of last adequate ^b tumor assessment before missed tumor assessment	Censor
Subjects still on study without PD or death as of data cut off	Date of last adequate ^b tumor assessment prior to or on date of data cut off	Censor

a: Earliest date among the two dates will be used in calculating the PFS.

b: Adequate tumor assessment is radiologic assessment of CR, PR, SD, non-CR/non-PD, or PD

c: Window of two or more missed tumor assessment is defined as duration between the last adequate tumor assessment and PD or death is ≥ 127 days, for scan schedule of every 8 weeks (± 7 days)

Duration of response (DOR) is defined as the time from the date of first evaluation of PR or CR to the date of first documented PD or death due to any cause (whichever occurs first). DOR will be calculated for each subject and shown in only subject data listings. Only subjects who achieved at least one PR or CR will be include in calculation of DOR. For subjects who do not have an event (documented PD or death from any cause), DOR will be censored. Censoring rules for DOR are shown in [Table 3](#).

Table 3 Censoring Rules of DOR

Situation	End Date	Censor/Event
Documented PD during the study	Date of the first assessment of the series of the tests that determined PD	Event ^a
Death during the study before PD	Date of death	Event ^a
Treatment discontinuation for other than PD or death with postbaseline tumor assessments	Date of last adequate ^b tumor assessment	Censor
New anticancer treatment started prior to PD or death	Date of last adequate ^b tumor assessment prior to or on date of new treatment	Censor
PD or death after two or more missed tumor assessments ^c	Date of last adequate ^b tumor assessment before missed tumor assessment	Censor
Subjects still on study without PD or death as of data cut off	Date of last adequate ^b tumor assessment prior to or on date of data cut off	Censor

a: Earliest date among the two dates will be used in calculating the DOR.

b: Adequate tumor assessment is radiologic assessment of CR, PR, SD, non-CR/non-PD, or PD

c: Window of two or more missed tumor assessment is defined as duration between the last adequate tumor assessment and PD or death is ≥ 127 days, for scan schedule of every 8 weeks (± 7 days)

DOR (days) = Date of first documented PD/ death/ Censored date – Date of first evaluation of PR or CR + 1.

Subject data listings will be provided.

5.4.2 Secondary Efficacy Analysis

Not applicable.

5.4.3 Other Efficacy Analysis

Not applicable.

5.5 Pharmacokinetic, Pharmacodynamic, Pharmacogenomic, and Other Biomarker Analyses

5.5.1 Pharmacokinetic Analyses

The Safety Analysis Set will be used for individual lenvatinib plasma concentrations and everolimus blood concentrations listings. The PK Analysis Set will be used for the summaries of lenvatinib plasma concentrations and everolimus blood concentrations and for summaries and listings of PK parameters.

5.5.1.1 Plasma or Blood Concentration and its PK Parameter Analysis

<Concentration>

Plasma concentration values for lenvatinib and blood concentration values for everolimus will be summarized using summary statistics (n, mean, standard deviation [SD], median, minimum [min] and maximum [max]) by nominal time point.

Plasma concentrations of lenvatinib and blood concentrations of everolimus will be listed for each subject by actual sampling time.

<PK Parameter>

PK parameters will be derived by non-compartmental analysis using WinNonlin software (version 6.2.1 or later) according to SWP-SOCS-006.02.

The following pharmacokinetic parameters for lenvatinib and everolimus will be calculated: C_{max} , t_{max} , $AUC_{(0-t)}$, $AUC_{(0-ti)}$, $AUC_{(0-inf)}$, $t_{1/2}$, CL/F , V_z/F , $C_{ss,max}$, $C_{ss,min}$, $t_{ss,max}$, $AUC_{(0-\tau)}$, CL_{ss}/F , $C_{ss,av}$, $R_{ac}(C_{max})$, $R_{ac}(AUC)$, PTF ratio.

Other PK parameters may be calculated as appropriate.

Summary statistics will be tabulated for the PK parameters of lenvatinib and everolimus. Summary statistics (n, mean, SD, median, min, and max) will be presented for all parameters (apart from t_{max} where mean and SD are not required). In addition, geometric mean and %CV will also be presented for all parameters apart from t_{max} .

PK parameters of lenvatinib and everolimus for each subject will be listed.

5.5.1.2 Pharmacokinetic Data Figures

The linear and semi-log plots of plasma concentration for lenvatinib and blood concentration for everolimus versus actual time will be displayed by individual subjects. The actual time will be plotted on the X axis and the concentrations of lenvatinib and everolimus will be plotted on the Y axis.

The linear and semi-log mean (+SD) plots of lenvatinib plasma concentration versus nominal time will be displayed. The nominal time will be plotted on the X axis and the mean (+SD) will be plotted on the Y axis on the same graph by visit (Cycle 1 Day 1 and Cycle1 Day 15).

The linear and semi-log mean (+SD) plots of everolimus blood concentration versus nominal time will be displayed. The nominal time will be plotted on the X axis and the mean (+SD) will be plotted on the Y axis on the same graph by visit (Cycle 1 Day 1 and Cycle1 Day 15).

5.5.2 Pharmacodynamic, Pharmacogenomic, and Other Biomarker Analyses

Not applicable.

5.6 Safety Analyses

The analysis for tolerability will be performed on the DLT Analysis Set. The Safety Analysis Set will be used for all other safety analyses. Safety data will be summarized on an “as treated” basis using summary statistics (e.g., n, mean, SD, median, Q1, Q3, minimum, maximum for continuous variables; number [percentage] for categorical variables). Safety variables include treatment-emergent adverse events (TEAEs), clinical laboratory parameters, vital signs, weight, LVEF, 12-lead ECG results, and ECOG PS. Study Day 1 for all safety analyses will be defined as the date of the first dose of lenvatinib.

5.6.1 Extent of Exposure

For lenvatinib and everolimus, the number of cycles, the cumulative number of cycles, duration of treatment per subject, number of subject months, total number of doses per subject, total doses per subject, dose intensity per subject, and relative dose intensity per subject will be summarized, separately. The calculations are below:

- Number of cycles = The last cycle with at least one study treatment dosing
- Duration of treatment (days) = Last dosing date – first dosing date + 1
- Duration of treatment (months) = (Last dosing date – first dosing date + 1) / (365.25/12)
- Number of subject months = (Total of Durations of treatment per subject) / (365.25/12)
- Total number of doses = Sum of days with study treatment dosing
- Total doses (mg) = Sum of all the actual dose
- Dose intensity (mg/days) = Total doses / Duration of treatment
- Relative dose intensity (%) = $100 \times \text{Dose intensity} / \text{defined starting dose for each dose group}$

The number (percentage) of subjects who experienced dose interruption, dose reduction of lenvatinib or everolimus will be provided. In addition, the cycle of first dose interruption, dose reduction, the number of subjects (percentage) with dose interruption, dose reduction by

cycle, the frequency of dose interruption, dose reduction during treatment of lenvatinib or everolimus will also be summarized.

Subject data listings will be provided.

5.6.2 Adverse Events

DLTs

The number (percentage) of subjects who experienced DLT will be summarized.

Adverse events (AE)

The AE verbatim descriptions (investigator terms from the CRF) will be classified into standardized medical terminology using the Medical Dictionary for Regulatory Activities (MedDRA). Adverse events will be coded to the MedDRA (Version 17.1 or higher) lower level term (LLT) closest to the verbatim term. The linked MedDRA preferred term (PT) and primary system organ class (SOC) will also be captured in the database.

A treatment-emergent adverse event (TEAE), defined in “[8.1 General Data Handling](#)”, will be included in summary tables. All AEs, treatment emergent or otherwise, will be presented in subject data listings.

The incidence of TEAEs will be reported as the number (percentage) of subjects with TEAEs by MedDRA SOC and PT. A subject will be counted only once within a SOC and PT, even if the subject experienced more than 1 TEAE within a specific SOC and PT. The number (percentage) of subjects with TEAEs will be summarized by highest grade according to common toxicity criteria for adverse events (CTCAE) ver. 4.03. The number (percentage) of subjects with TEAEs with CTCAE grade 3 or above will also be summarized by highest grade.

The number (percentage) of subjects with treatment-related TEAEs will be summarized by MedDRA SOC and PT. Treatment-related TEAEs include those events considered by the investigator to be related to lenvatinib or everolimus. The number (percentage) of subjects with treatment-related TEAEs will be summarized by highest CTCAE grade. The number (percentage) of subjects with treatment-related TEAEs with CTCAE grade 3 or above will also be summarized by highest grade.

The number (percentage) of subjects with DLTs will be summarized by MedDRA SOC and PT. All DLTs will be presented in subject data listings.

The number (percentage) of subjects with TEAEs leading to death, treatment-emergent serious adverse events (SAEs) will be summarized by MedDRA SOC and PT. The number (percentage) of subjects with treatment-related TEAEs leading to death, treatment-related treatment-emergent SAEs will also be summarized by MedDRA SOC and PT. A subject data listing of all serious adverse events, AEs leading to death will be provided.

The number (percentage) of subjects with TEAEs leading to dose reduction of lenvatinib and/or everolimus (A TEAE leading to discontinuation of only everolimus will be counted as a TEAE leading to dose reduction of lenvatinib and/or everolimus in this table), and dose interruption of lenvatinib and/or everolimus will be summarized by MedDRA SOC and PT.

As well as TEAEs, the number (percentage) of subjects with treatment-related TEAEs leading to dose reduction of lenvatinib and/or everolimus (A treatment-related TEAE leading to discontinuation of only everolimus will be counted as a treatment-related TEAE leading to dose reduction of lenvatinib and/or everolimus), and dose interruption of lenvatinib and/or everolimus will be summarized by MedDRA SOC and PT.

The number (percentage) of subjects with TEAEs leading to discontinuation from lenvatinib, dose reduction of lenvatinib, and dose interruption of lenvatinib, discontinuation from everolimus, dose reduction of everolimus, and dose interruption of everolimus will also be summarized by MedDRA SOC and PT.

In addition to TEAEs, the number (percentage) of subjects with treatment-related TEAEs leading to discontinuation from lenvatinib, dose reduction of lenvatinib, and dose interruption of lenvatinib will be summarized by MedDRA SOC and PT. For these analyses, treatment-related TEAEs include those events considered by the investigator to be related to lenvatinib. The number (percentage) of subjects with treatment-related TEAEs leading to discontinuation from everolimus, dose reduction of everolimus, and dose interruption of everolimus will also be summarized by MedDRA SOC and PT. For these analyses, treatment-related TEAEs include those events considered by the investigator to be related to everolimus.

A subject data listing of AEs leading to discontinuation from study treatment, dose reduction and dose interruption will be provided.

An overview table, including the incidence of and the number of subjects with TEAEs, treatment-related TEAEs, TEAEs with CTCAE grade 3 or above, treatment-emergent SAEs, deaths, and those TEAEs leading to treatment discontinuation, dose reduction, or dose interruption, and corresponding treatment-related TEAEs in above categories will be provided.

5.6.3 Laboratory Values

Laboratory results will be summarized using Système International (SI) units. For all quantitative parameters listed in protocol Section 9.5.1.3.5, the actual value and the change from baseline to each postbaseline visit, the highest and lowest postbaseline values will be summarized by visit using summary statistics. Qualitative parameters will be summarized by number and percentage of subjects, and changes from baseline to each postbaseline visit and the highest postbaseline result will be reported using shift tables. Percentages will be based on the number of subjects with both nonmissing baseline and relevant postbaseline results.

Laboratory test results will be assigned a low/normal/high (LNH) classification according to whether the value is below (L), within (N), or above (H) the laboratory parameter's reference range. The result of LNH classification will be provided in a subject data listing.

Laboratory parameters will be graded by CTCAE ver. 4.03 in "[13 APPENDICES](#)". Changes from CTCAE grade at baseline to each postbaseline visit and worst postbaseline will be reported using shift tables. As for thyroid stimulation hormone, values at baseline and worst postbaseline will be categorized into ≤ 0.5 , $>0.5 - 2.0$, $>2.0 - 5.5$, >5.5 ($\mu\text{IU/mL}$) and summarized.

CTCAE ver. 4.03 will be used to identify subjects with Treatment-emergent markedly abnormal laboratory value (TEMAV). TEMAV is defined as a value with postbaseline value with a grade increase from baseline by 2 or higher. (i.e., Increasing grade 0 to 2 or higher, grade 1 to 3 or higher, grade 2 to 4 or 5.) For phosphate, TEMAV is defined as a value with postbaseline value with a grade increase from baseline by 3 or higher. The number (percentage) of subjects with TEMAV (markedly abnormal high/low) will be summarized by visit. When displaying the incidence of TEMAVs, each subject will be counted once in the laboratory parameter high and in the laboratory parameter low categories, as applicable.

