#### 9.7.1.1 Study Endpoints

##### **PRIMARY ENDPOINTS**

Dose limiting toxicity (DLT)

Safety variables (AEs, clinical laboratory results, vital signs, weight, ECG, ECOG-PS, LVEF)

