### **LABORATORY VALUES**

Laboratory results will be summarized using Système International (SI) units. For all quantitative parameters listed in Section 9.5.1.3.3, the actual value and the change from baseline to each postbaseline visit will be summarized by visit using descriptive statistics. Qualitative parameters will be summarized by number and percentage of subjects, and changes from baseline to each postbaseline visit will be reported using shift tables. Percentages will be based on the number of subjects with both nonmissing baseline and relevant postbaseline results.

Laboratory test results will be assigned a low/normal/high (LNH) classification according to whether the value was below (L), within (N), or above (H) the laboratory parameter's reference range. CTCAE v4.03 will be used to identify subjects with treatment emergent markedly abnormal laboratory values (TEMAV). A TEMAV is defined as a postbaseline value with an increase from baseline to a grade of 2 or higher. When displaying the incidence of TEMAVs, each subject may be counted once in the laboratory parameter high and in the laboratory parameter low categories, as applicable.

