Calcium, serum-low (hypocalcemia)	2.0 - <LLN (mmol/L) (i.e., 8.0 mg/dL - <LLN) *	1.75 - <2 (mmol/L) (i.e., 7.0 - <8.0 mg/dL) *	1.5 - <1.75 (mmol/L) (i.e., 6.0 - <7.0 mg/dL) *	<1.5 (mmol/L) (i.e., <6.0 mg/dL) *	Death
Calcium, serum-high (hypercalcemia)	>ULN - 2.9 (mmol/L) (i.e., >ULN - 11.5 mg/dL) *	>2.9 - 3.1 (mmol/L) (i.e., >11.5 - 12.5 mg/dL) *	>3.1 - 3.4 (mmol/L) (i.e., >12.5 - 13.5 mg/dL) *	>3.4 (mmol/L) (i.e., >13.5 mg/dL) *	Death
Cholesterol (high)	>ULN - 7.75 mmol/L	>7.75 - 10.34 mmol/L	>10.34 - 12.92 mmol/L	>12.92 mmol/L	—
CPK (high)	>ULN - 2.5 x ULN	>2.5 x ULN - 5 x ULN	>5 x ULN - 10 x ULN	>10 x ULN	—
Creatinine (high)	>1 - 1.5 x baseline; >ULN - 1.5 x ULN	>1.5 - 3.0 x baseline; >1.5 - 3.0 x ULN	>3.0 x baseline; >3.0 - 6.0 x ULN	>6.0 x ULN	—
Glucose, serum-low (hypoglycemia)	3 - <LLN (mmol/L)	2.2 - <3 (mmol/L)	1.7 - <2.2 (mmol/L)	<1.7 (mmol/L)	Death
Glucose, serum-high (hyperglycemia)	ULN - 8.9 (mmol/L)	>8.9 - 13.9 (mmol/L)	>13.9 - 27.8 (mmol/L)	>27.8 (mmol/L)	Death

Lab Parameter	NCI Common Terminology Criteria for Adverse Events (CTCAE) - SI Units				
	Grade 1	Grade 2	Grade 3	Grade 4	Grade 5
Lipase (high)	>ULN - 1.5 x ULN	>1.5 - 2.0 x ULN	>2.0 - 5.0 x ULN	>5.0 x ULN	—
Magnesium (low)	<LLN - 0.5 (mmol/L)	<0.5 - 0.4 (mmol/L)	<0.4 - 0.3 (mmol/L)	<0.3 (mmol/L)	Death
Magnesium (high)	>ULN - 1.23 (mmol/L)	—	>1.23 - 3.30 (mmol/L)	>3.30 (mmol/L)	Death
Triglyceride (hypertriglyceridemia) (high)	1.71 - 3.42 (mmol/L)	>3.42 - 5.7 (mmol/L)	>5.7 - 11.4 (mmol/L)	>11.4 (mmol/L)	Death
Phosphate, serum-low (hypophosphatemia)	0.8 - <LLN (mmol/L)	0.6 - <0.8 (mmol/L)	0.3 - <0.6 (mmol/L)	<0.3 (mmol/L)	Death
Potassium, serum-low (hypokalemia)	3.0 - <LLN (mmol/L)	—	2.5 - <3.0 (mmol/L)	<2.5 (mmol/L)	Death
Potassium, serum-high (hyperkalemia)	>ULN - 5.5 (mmol/L)	>5.5 - 6.0 (mmol/L)	>6.0 - 7.0 (mmol/L)	>7.0 (mmol/L)	Death
Sodium, serum-low (hyponatremia)	130 - <LLN (mmol/L)	—	120 - <130 (mmol/L)	<120 (mmol/L)	Death
Sodium, serum-high (hypernatremia)	>ULN - 150 (mmol/L)	>150 - 155 (mmol/L)	>155 - 160 (mmol/L)	>160 (mmol/L)	Death
Urinalysis					
Proteinuria (high)	1+ proteinuria; urinary protein <1.0 g/24 hrs	≥2+ proteinuria; urinary protein 1.0 - 3.4 g/24 hrs	urinary protein ≥3.5 g/24 hrs	—	—

* Corrected serum calcium by albumin should be referred. If serum albumin is <4.0 g/dL, the corrected calcium will be calculated using the following formula:
Corrected calcium (mg/dL) = Total calcium (mg/dL) - 0.8 x [Albumin (g/dL) - 4]

SIGNATURE PAGE

Author:		

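### SAP 5.6.3 narrows the protocol's definition of a markedly abnormal laboratory value (TEMAV), so the count can only be lower or equal, and SAP Section 7 logs the change as an addition without a specific reason

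*SAP*

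**What the plan says.** Protocol 9.7.1.9 (Laboratory Values) already contains a definition: "A TEMAV is defined as a postbaseline value with an increase from baseline to a grade of 2 or higher".

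SAP 5.6.3 has a different one: "TEMAV is defined as a value with postbaseline value with a grade increase from baseline by 2 or higher". It lists the shifts it means: "Increasing grade 0 to 2 or higher, grade 1 to 3 or higher, grade 2 to 4 or 5". It then makes one exception: "For phosphate, TEMAV is defined as a value with postbaseline value with a grade increase from baseline by 3 or higher". Both documents grade with CTCAE v4.03.

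SAP Section 7 lists the TEMAV analysis and its definition among items newly introduced relative to the protocol. The only purpose given is a general one that covers the whole list, namely to set up the analyses for the study report. Nothing there explains the two-grade threshold or the phosphate exception.

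The SAP also plans full grade tables: "Changes from CTCAE grade at baseline to each postbaseline visit and worst postbaseline will be reported using shift tables".

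**The concern.** One word separates the definitions: the protocol asks whether the value worsened to Grade 2, the SAP whether it worsened by 2 grades. A table headed TEMAV built to the SAP would not report what the protocol calls a TEMAV.

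Protocol 9.7.1.1 puts laboratory results inside the primary endpoint, under "Safety variables (AEs, clinical laboratory results, vital signs, weight, ECG, ECOG-PS, LVEF". The change also works in one direction only, since it can lower a safety count but never raise it. Someone checking Section 7 for departures from the protocol would not learn that an existing definition had been narrowed. Section 7 is able to say such things: it records the waterfall plot as replaced and gives a reason for dropping the tumor-marker analysis.

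**Working it through.** The documents give no numerical figure on this point to reproduce. The check sets the two rules side by side.

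**Rules.** Let b be the baseline grade and p the postbaseline grade. Grade 5 (death) is left out because no laboratory value defines it.
- Protocol 9.7.1.9: p > b and p ≥ 2.
- SAP 5.6.3, general: p − b ≥ 2.
- SAP 5.6.3, phosphate: p − b ≥ 3.

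**Direction.** Since b ≥ 0, p − b ≥ 2 implies p ≥ 2 and p > b. So every SAP TEMAV is a protocol TEMAV. The reverse fails, as the possible shifts show:

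| Shift | Protocol | SAP general | SAP phosphate |
|---|---|---|---|
| 0→2 | yes | yes | no |
| 0→3 | yes | yes | yes |
| 0→4 | yes | yes | yes |
| 1→2 | yes | no | no |
| 1→3 | yes | yes | no |
| 1→4 | yes | yes | yes |
| 2→3 | yes | no | no |
| 2→4 | yes | yes | no |
| 3→4 | yes | no | no |
| Shifts counted | 9 | 6 | 3 |

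These are kinds of shift for a parameter with Grades 1 to 4, not expected numbers of subjects.

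**Hemoglobin.** Inclusion criterion 9a (Protocol 9.3.1) admits 9.0 g/dL, that is 90 g/L. In SAP 13.1, low hemoglobin is Grade 2 from 80 to below 100 g/L and Grade 3 below 80 g/L, with no Grade 4. A subject entering at 90 to below 100 g/L who falls below 80 g/L moves 2→3. The protocol rule is met (3 > 2 and 3 ≥ 2). The SAP rule is not (3 − 2 = 1), and the row has no higher laboratory grade to reach. Exclusion criterion 3 (Protocol 9.3.2) narrows this group, because Grade 2 anemia that is unresolved toxicity of prior anticancer therapy is excluded, but it does not close it.

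**Phosphate.** In SAP 13.1, Grade 2 is 0.6 to below 0.8 mmol/L, Grade 3 is 0.3 to below 0.6, and Grade 4 is below 0.3. Values that count:
- Baseline Grade 0: protocol below 0.8; SAP below 0.6.
- Baseline Grade 1: protocol below 0.8; SAP below 0.3.
- Baseline Grade 2: protocol below 0.6; SAP none, since the highest laboratory grade is 4 and 4 − 2 = 2.

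A fall from normal to 0.7 mmol/L is thus a TEMAV under the protocol but not under the SAP. The eligibility criteria set no phosphate limit.

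**Liver enzymes.** Inclusion criterion 9e allows ALP, AST and ALT up to 5.0 × ULN with liver metastasis, so baseline Grade 2 is possible. From there the protocol rule is met above 5.0 × ULN (Grade 3), the SAP rule only above 20.0 × ULN (Grade 4).

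**Weight of one subject.** With 6 to 12 subjects per initial dose group, each affected subject moves a percentage by 1/12 = 8.3 to 1/6 = 16.7 points.

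**Recovering the protocol count.** For each parameter, sum the cells of the worst-postbaseline shift table where the worst grade exceeds baseline and is at least 2. This assumes one table per row of SAP 13.1, so that high and low directions are kept apart.

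**The case against.** The best case for the SAP has four parts, and most of it stands as a limit on the impact.

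- *The item is disclosed.* Section 7 does name the TEMAV definition and gives a general purpose for its list, so a reader who infers that the SAP says nothing at all goes too far. What is missing is a statement that a protocol definition changed, and a reason specific to that change.
- *The threshold has a precedent.* The laboratory adverse-event criteria in Protocol 9.5.1.3 also use a worsening of two or more grades. That is a separate rule, however. The SAP does not cite it, and its named exceptions (lymphocytes, albumin, cholesterol, glucose) do not include phosphate.
- *No laboratory information is lost.* This is right. The shift tables, themselves an SAP addition, still show every dropped shift, and laboratory changes that meet the adverse-event criteria enter the adverse-event tables. A reader might infer that a safety signal is being hidden; the documents do not support that.
- *Nothing hangs on TEMAV.* Also right. The study tests no hypothesis, and tolerability is judged on DLTs and unacceptable toxicities.

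A reader might also try to size the effect by tallying lost shifts over every row of SAP 13.1. That would overstate it. Eligibility rules out baseline Grade 2 or 3 for neutrophils, platelets, bilirubin and cholesterol, and baseline Grade 3 for ALP, AST and ALT. High hemoglobin is graded from baseline when baseline exceeds ULN, so its lost shifts are doubtful. Nor do the documents show that laboratory results prompted the change.

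**Conclusion.** The contradiction is real. SAP 5.6.3 replaces the protocol's TEMAV rule with a strictly narrower one under the same name, and Section 7 misdescribes this as an addition. The direction is certain: the SAP count is lower than or equal to the protocol count, never higher. This rests on identical CTCAE v4.03 grading under both rules, which both documents specify, and on the plain reading of the protocol rule as any worsening that ends at Grade 2 or above.

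The size cannot be estimated, because the documents contain no laboratory shift data. The number of affected subjects may be zero. The consequence is limited to one descriptive table within the primary safety endpoint. A two-grade flag is defensible if declared as a change; the three-grade rule for phosphate has no stated basis. The correction should be made, but no conclusion of the trial depends on it.

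**What to change.** In SAP 5.6.3, report TEMAV by the protocol definition for every parameter, phosphate included: any postbaseline worsening from baseline that reaches Grade 2 or above. If the two-grade rule (three for phosphate) is kept, show it as an additional line under its own label. In SAP Section 7, state that the protocol's TEMAV definition was changed or supplemented, and give the reason for each threshold.

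The cost is one sentence in 5.6.3, one derivation line and one line in Section 7. Showing both counts needs one extra derivation, and the TEMAV counts may come out somewhat higher than under the present SAP rule.
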